### **9.11.1 Adverse Events**

Adverse events will be tabulated on both an event basis (total number of events), and on a subject-basis reporting treatment-emergent events.

### **9.11.2 Missing and Partial Adverse Event Dates**

The start dates for AEs are important for the:

1. Treatment emergent algorithm.
2. The designation of unique AE occurrences.

Completely missing or partially missing adverse event onset dates will be imputed as follows after due diligence to obtain accurate adverse event information has failed.

If the adverse event start date is completely missing then the adverse event will be considered treatment emergent unless it can be determined that the adverse event end date occurred prior to the study procedure. If this is the case, the adverse event will not be considered treatment emergent.

If the adverse event start date is partially missing and the partial date is not sufficient to determine if the event occurred after the study procedure, then the adverse event will be considered treatment emergent unless it can be determined that the adverse event end date occurred prior to the study procedure.

### **9.11.3 Summaries of Adverse Events**

All summaries of AEs will be based on treatment-emergent AEs. Adverse events will be mapped to preferred terms and body systems using the Medical Dictionary for Regulatory Activities (MedDRA) coding dictionary. The number and percentage of subjects experiencing AEs will be summarized by system organ class and preferred term. Summaries by maximum severity and

relationship to study treatment will also be provided. Serious AEs and AEs leading to discontinuation from the study will be presented by system organ class and preferred term.

#### **9.11.4 Overall Summary of Adverse Events**

The Overall Summary of Treatment Emergent Adverse Events contains the number and percentage of subjects who:

- have any treatment emergent adverse events
- have any treatment emergent adverse events at least possibly related to the study device
- have any treatment emergent adverse events at least possibly related to the study procedure
- have any treatment emergent adverse events presented by maximum severity
- have any treatment emergent serious adverse events
- have any treatment emergent serious adverse events at least possibly related to the study device
- have any treatment emergent serious adverse events at least possibly related to the study procedure
- have any treatment emergent adverse events leading to discontinuation of the study
- have any treatment emergent adverse events leading to death
- have any treatment emergent adverse events leading to death that are at least possibly related to the study device
- have any treatment emergent adverse events leading to death that are at least possibly related to the study procedure.

#### **9.11.5 Summary of Adverse Events by System Organ Class and Preferred Term**

The Summary of Treatment Emergent Adverse Events by System Organ Class and Preferred Term will contain the primary presentation of the adverse event data. This table is prepared without regard to causality or relationship to the study procedure. Subjects will be counted only once at the system organ class level and will be counted once for each applicable preferred term; multiple occurrences of the same preferred term for a subject will be counted only once. System organ classes, and preferred terms within system organ class, will be displayed alphabetically. In addition, an exact 95% confidence interval for the overall adverse event rate will be displayed.

#### **9.11.6 Assessment of Severity**

All adverse events, both serious and non-serious, will be assessed for severity or intensity. The intensity of all AEs will be graded as mild, moderate, or severe.

The Summary of Treatment Emergent Adverse Events by System Organ Class and Preferred Term with Respect to Event Severity provides the presentation of adverse events with respect to the severity or intensity of the event. Subjects with multiple occurrences of the same system organ class or preferred term will be summarized at the maximum severity reported for that adverse event. The number and percentage of subjects experiencing AEs for each body system and preferred term will be displayed.

#### **9.11.7 Assessment of Relationship to the Device**

The CEC will adjudicate each AE and make the determination of relationship to study device using the definitions in Section 6.1.

The Summary of Treatment Emergent Adverse Events by System Organ Class, Preferred Term, and Relationship to the Study device provides the presentation of adverse events by relationship to the study device. Subjects with multiple occurrences of the same system organ class or preferred term will be summarized using the event with the strongest relationship to the study device. The number and percentage of subjects experiencing each system organ class and preferred term will be displayed.

#### **9.11.8 Assessment of Relationship to the Procedure**

The CEC will adjudicate each AE and make the determination of relationship to study procedure using the definitions in Section 6.1.

The Summary of Treatment Emergent Adverse Events by System Organ Class, Preferred Term, and Relationship to the Study Procedure provides the presentation of adverse events by relationship to the study procedure. Subjects with multiple occurrences of the same system organ class or preferred term will be summarized using the event with the strongest relationship to the study procedure. The number and percentage of subjects experiencing each system organ class and preferred term will be displayed.

#### **9.11.9 Summary of Adverse Events Leading to Discontinuation**

The Summary of Treatment Emergent Adverse Events Leading to Study Discontinuation by System Organ Class and Preferred Term displays all treatment-emergent adverse events resulting in an action taken of 'Discontinued'. Subjects will be counted only once at the system organ class level and will be counted once for each applicable preferred term; multiple occurrences of the same preferred term for a subject will be counted only once. The number and percentage of subjects experiencing each body system and preferred term leading to discontinuation will be displayed.

#### **9.11.10 Summary of Serious Adverse Events**

Adverse event incidence rates by system organ class and preferred term will be summarized for subjects who report a serious adverse event. Subjects with multiple SAEs will be counted only once at the system organ class level and will be counted once for each applicable preferred term; multiple occurrences of the same preferred term for a subject will be counted only once. The number and percentage of subjects experiencing each system organ class and preferred term will be displayed. In addition, an exact 95% confidence interval for the overall serious adverse event rate will be displayed.

### **9.12 Imaging**

The presentation of imaging results will focus on the descriptive summaries at pre-procedure and post-procedure, and during the follow-up procedure. All subjects in the ITT population who have a pre-procedure, post-procedure and a follow-up assessment will be included in the presentation of the imaging data.

For each quantitative imaging parameter, the results at each time point and the change from pre-procedure results will be summarized using descriptive statistics: N, mean, standard deviation, median, and range. In addition to the change from pre-procedure results, the shift from baseline to the post-baseline visits will be summarized in tabular form for each parameter. Subjects will be classified at baseline and the post-baseline visit in one of the following categories based on a comparison of the imaging result. A shift table will be constructed in which each subject is cross-classified based upon the reference range categories. The number and percentage of subjects in each shift table cell will be displayed.

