## **6 ADVERSE EVENTS**

The following adverse events will be collected during the course of the study on the eCRFs.

- All Adverse Events (AE) with an underlying neurological cause (Neurological Adverse Events)
- All Device Related Adverse Events
- All Procedure Related Adverse Events
- All Serious Adverse Events (SAE's)

Adverse event status will be evaluated throughout the study. These will include new events occurring after the point of consent in the study until a subject exits the study. Subjects who are enrolled, underwent surgery to implant to study device but did not have the Pipeline™ device implanted for any reason will be followed for 30 days and relevant safety events will be collected. Investigators must obtain all information available to determine the causality and outcome of the AE and to assess whether it meets the criteria for classification as a serious and/or unexpected event requiring notification to the Sponsor, regulatory agency, and as applicable, IRB/EC, within the specified reporting timeframe. AEs will be categorized using the definitions in **Section 6.1**.

All study AEs, as well as the treatment and follow-up required, should be documented in the subject's medical records and in the eCRF. All study AEs will be followed by the Investigator until resolution or until the end of the 3-year follow-up. A list of potential anticipated adverse events is provided in **Section 10.2**.

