#### 8.2.1 Baseline anatomy

Baseline imaging will be reviewed to assess baseline aneurysm and parent artery characteristics.

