### 8.2.3 Parent Artery Stenosis

Post-procedure angiograms will be reviewed to assess stenosis in the parent artery across the entire Pipeline™ device. Vessel stenosis will be measured and judged according to the scale in **Table 6**.

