### **9.9 Analysis of the Additional Data**

The device-related neurologic adverse event rate at 1 year post-procedure will be tabulated for the ITT population and presented using counts, percentages, and 2-sided 95% exact binomial confidence intervals. The mRS score at 1 year will be dichotomized ( $\geq 2$  vs.  $< 2$ ) and summarized using counts, percentages, and 2-sided 95% exact binomial confidence intervals. Aneurysm occlusion will be tabulated for the Full Analysis Set and presented using counts, percentages, and 2-sided 95% exact binomial confidence intervals. The proportion of subjects who experience recurrence and require retreatment will be summarized using counts, percentages, and 2-sided 95% exact binomial confidence intervals. Procedure time, radiation exposure (dosage and time) and number of Pipeline™ devices utilized will be summarized using descriptive statistics (N, mean, median, standard deviation, minimum and maximum value, and 95% 2-sided confidence limits).

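### Section 9.12 shows baseline and immediate post-procedure imaging only for subjects who also have a later follow-up image (minor; descriptive tables only)

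*Combined protocol and SAP*

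**What the plan says.** Section 9.12 describes the imaging presentation as "descriptive summaries at pre-procedure and post-procedure, and during the follow-up procedure". Its population is given in one sentence: "All subjects in the ITT population who have a pre-procedure, post-procedure and a follow-up assessment will be included". It then specifies, for each quantitative parameter, that "the results at each time point and the change from pre-procedure results will be summarized using descriptive statistics", and adds shift tables from baseline to later visits. No sentence in the plan gives the baseline or post-procedure images a different population.

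Other sections bear on who can satisfy that rule:

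- **Core laboratory readings (8.2).** For baseline, "Baseline imaging will be reviewed to assess baseline aneurysm and parent artery characteristics". For the implant, "Post-procedure angiograms will be reviewed to assess stenosis in the parent artery across the entire" device.
- **Timing of images.** Pre- and post-treatment angiograms are required on the procedure day (Table 5, note 5). At 180 days an angiogram is sent only if done as standard care (5.7.2). The 1-year visit is the first at which the visit text requires follow-up angiography (5.7.3). Angiograms at other times are sent to the core laboratory if they are done (5.8).
- **Attempted but not implanted.** Section 9.3 places a subject in ITT once deployment is attempted. Under Section 6, a subject who had the procedure without receiving the device "will be followed for 30 days and relevant safety events will be collected".
- **Separate populations.** The primary effectiveness analysis (9.5) is on the Full Analysis Set (FAS). In 9.9, "Aneurysm occlusion will be tabulated for the Full Analysis Set".

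**The concern.** Requiring a baseline and a later image is sensible for a change score or a shift table, where both values are needed. It is not sensible for a table of the baseline values themselves, or of the readings at the end of the procedure. There it makes the display of a day-0 measurement depend on something that happens months later.

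The subjects removed are not a random subset by design. They include people who die or withdraw before any follow-up angiogram, and people in whom implantation failed. A reader who wants the anatomy of the treated population, or parent-artery stenosis straight after implantation, would see a selected group labelled ITT. The three-way condition also works in the other direction: a usable follow-up reading is discarded if the post-procedure image is missing or unreadable.

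At stake is the accuracy of the descriptive account of anatomy and immediate result.

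**Working it through.** Section 9.12 states no figure, so the main check is a reading of the text. The arithmetic only shows how large the effect could be.

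**Step 1: what the rule requires.** The conditions are joined by *and*: a pre-procedure image, a post-procedure image and a follow-up image. The sentence says that such subjects will be included. It does not say *only*, but it is the sole inclusion rule for the imaging presentation and so acts as a restriction.

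**Step 2: which tables it governs.** Section 9.12 lists results at each time point as well as changes and shifts. The rule therefore reaches the pre-procedure and post-procedure summaries.

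**Step 3: who fails it despite having day-0 data.**

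- A subject who dies or withdraws before 1 year with no standard-care or unscheduled image.
- Most subjects with an attempted but failed implant. They are in ITT, but 30 days of follow-up for safety events would not normally produce a follow-up image. Section 5.4 allows a later placement, hence *most*.
- A subject with a valid follow-up image but no usable post-procedure image.

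I took image timing from the visit text in 5.7, because the imaging row of the schedule table does not align reliably in the extracted text.

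**Step 4: the denominator for the illustration.** Section 9.3 gives 141 treated subjects. This reproduces from Table 7: it is the smallest n for which the one-sided 97.5% Clopper-Pearson upper limit is below 15% at an observed 9%, allowing a non-integer event count (0.09 × 141 = 12.69; upper limit 0.1499).

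**Step 5: how many subjects leave the day-0 tables.** The documents give no missing-image rate, so the share m without a follow-up image is assumed to lie between 2% and 20%. Removed k = 141 × m, rounded; shown = 141 − k.

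| m (assumed) | Removed | Shown |
|---|---|---|
| 2% | 3 | 138 |
| 5% | 7 | 134 |
| 10% | 14 | 127 |
| 15% | 21 | 120 |
| 20% | 28 | 113 |

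**Step 6: how far a day-0 proportion could move.** Suppose a baseline or post-implant feature is present in 14 of 141 subjects (9.9%; an invented count). After k are removed, the displayed proportion lies between max(14 − k, 0)/(141 − k), when as many as possible of those removed have the feature, and 14/(141 − k), when none do.

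- m = 2%: 11/138 = 8.0% to 14/138 = 10.1%.
- m = 5%: 7/134 = 5.2% to 14/134 = 10.4%.
- m = 10%: 0/127 = 0.0% to 14/127 = 11.0%.

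These are bounds. The true figure of 9.9% lies inside each range, so the direction of any error cannot be read from the plan.

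**The case against.** The case for leaving 9.12 alone has real force.

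- **Nothing inferential depends on it.** Both primary tests have their own population and missing-data rules, and 9.9 puts occlusion on the FAS. Section 9.1 puts all recorded data in the listings, and 9.10 tabulates withdrawals with reasons. This stands, and it is why the point is minor. Listings do not replace a summary table, however, and although 9.1 summarises clinical and high-risk factors on ITT, it does not promise core-laboratory anatomy.
- **The scope of 9.12 is not fully stated.** Its time-point sentence concerns quantitative parameters, while the Roy grade and the stenosis categories of Table 6 are categorical. This stands in part: 9.12 does not name its parameters. But its population sentence covers the imaging data as a whole, and 8.2.3 says that stenosis is measured as well as graded.
- **Attrition may be small.** Any follow-up image seems to satisfy the rule, including a standard-care 180-day angiogram, and a major stroke does not preclude angiography. This stands. A reader might take the planning range for safety events (5% to 9% of 141, or about 7 to 13 subjects) as the number lost. The documents do not support that: they do not say that these subjects go without images.
- **Failed implants have no in-device reading to lose.** Correct; only their baseline anatomy is affected.

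A reader might also infer that the rule inflates 1-year occlusion or bears on the 50% goal. It does neither. Section 9.5 counts FAS subjects who miss the 1-year evaluation as successes and separately plans a worst-case analysis counting early withdrawals as failures; neither passes through 9.12. A subject with no 1-year image would be absent from a 1-year table of observed images under any rule, including the one proposed below.

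**Conclusion.** The point holds as a minor defect in the descriptive analysis. Read as written, 9.12 conditions pre-procedure and post-procedure imaging summaries on a later image, and drops some follow-up readings because another image is missing. No other section supplies the tables that are lost.

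The size is unknown. With 141 subjects and an assumed 2% to 20% lacking a follow-up image, 3 to 28 would leave the day-0 tables; subjects lost only for want of a post-procedure image would add to that. It is plausible that those removed differ from those shown, since early deaths and withdrawals are among them, but the documents link neither anatomy nor post-implant stenosis to missing follow-up. The direction of bias is therefore not established. Neither primary conclusion, nor the FAS occlusion table, nor the listings are affected.

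**What to change.** Replace the inclusion sentence in 9.12 with a rule by time point:

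- Summarise each time point in all subjects with an evaluable core-laboratory image at that time point: ITT for pre-procedure anatomy, FAS for post-procedure and follow-up readings.
- At each time point, show the number evaluable out of N and the reasons for missing images (death, withdrawal, not done, unreadable).
- Limit only the change-from-baseline and shift tables to subjects with both images of the pair.

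This also removes the need to decide which image counts as the qualifying follow-up assessment. It requires no new data or procedures and does not touch sample size or alpha. The cost is that denominators differ by visit, so each table must show its own n and readers should not treat differences between visits as within-subject change; the paired tables serve that purpose.

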## 10 RISK/BENEFIT

### 10.1 Potential Benefits

Embolization with the Pipeline™ device can be life-saving, partially or totally curative, and can reduce symptoms. Effectiveness can be measured by angiographic evidence of aneurysm occlusion and the amount of occlusion can be classified by the 3-point Scale of Roy. The greatest Pipeline™ device clinical benefit includes a completely occluded aneurysm which does not re-form and completely eliminates all associated symptoms. Intermediate benefits include stabilizing the aneurysm and providing symptomatic relief. Studies on endovascular treatments options like stent coiling have reported that complete occlusion has been achieved in 46%-75% of small and medium wide-necked aneurysms at one year post procedure so flow diverters such as Pipeline™ device would increase the likelihood that the procedure will provide full benefits to the subjects, without leaving behind coil mass which may cause significant symptoms following treatment.

### 10.2 Potential Risks

Potential risks associated with Pipeline™ device use, general anesthesia, catheterization and diagnostic imaging for subjects with intracranial aneurysms are outlined below.

#### Risks associated with placement of the Pipeline™ device:

Possible	

• Embolism

• Headache

• Hematoma

• Hemorrhage, intracranial

• Hemorrhage, non-intracranial

• In-stent stenosis

• Pain

• Parent artery stenosis

• Thromboembolic events

• Vision impairment

Infrequent	

• Amaurosis fugax (temporary loss of vision in one eye)

• Aneurysm rupture

• Arrhythmia

	

• AV fistula

• Blindness

• Blood vessel perforation / rupture / occlusion

• Carotid cavernous fistula

• Cranial neuropathy

• Death

• Dizziness / tinnitus

• Groin injury (including bleeding, bruising, infection, pain)

• In-stent occlusion

• Infection

• Ischemia

• Mass effect

• Nausea / vomiting

• Neurological deficits

• Palsy / muscle weakness

• Pseudoaneurysm

• Ptosis

• Stroke, hemorrhagic

• Stroke, ischemic

• Transient ischemic attack

• Thrombosis / occlusion of the parent artery

• Vasospasm (acute narrowing of the blood vessel due to irritation from the tubes being placed in the blood vessel)

Rare	

• Allergic reaction to medications and/or dye

• Coma

• Device fracture

• Device migration or misplacement.

• Hydrocephalus

• Seizure

Risks associated with DAPT required for flow diverter treatment:

- Abnormal bleeding
- Abnormal blood clotting
- Adverse reaction to the anesthesia
- Allergic reaction to medications (can range from a mild reaction such as rash or facial flushing to a more severe reaction such as difficulty breathing)
- Abdominal pain, nausea, vomiting and dyspepsia
- Gastritis and gastric ulcer
- Tinnitus
- Syncope
- Death

Risks associated with imaging required for flow diverter treatment:

- Reddening of the skin, blistering and even ulceration
- Developing a radiation-induced cancer later in life
- Renal injury associated with contrast

Risks associated with Clinical Research

Moreover, as in all clinical studies, confidentiality of protected health information may be breached due to study-related activities beyond those of routine clinical care.

### **10.3 Risk Mitigation**

Several safeguards are incorporated into the study to minimize subject risk. All preclinical device testing for the implantable braid and the single use delivery system are performed in accordance with regulations and recognized standards. All test results have passed the required specifications supporting reasonable safety for this clinical product.

At each investigational site, the study will be conducted under the direction of a qualified physician experienced with endovascular procedures including intracranial aneurysm repair and will have completed at least 20 cases with the Pipeline™ device. All participating investigators have experience conducting clinical research and have adequate personnel to assure compliance to the study protocol.

Subjects will be monitored closely as part of the study to allow for detection of adverse events, should they be present. Thus, in turn, should allow for early treatment, if necessary. Personally identifying subject information will not be collected on electronic Case Report Forms (eCRFs) or other study-related documentation to be provided to the Sponsor.

All study data will be monitored by individual site and combined sites. Clinical outcomes of all study subjects will be routinely monitored by the Sponsor during the course of the study. Safety endpoint related events will be reviewed and adjudicated by an independent CEC. In the event of unforeseen or increased risks to subjects encountered during the course of the study, the study may be suspended or terminated.

